### 7.4 Age

Age will be derived as date of informed consent minus date of birth then divided by 365.25 and presented in years.

### 7.5 Duration of Chronic Cough

Duration of chronic cough (years) will be derived as year of informed consent minus year of start date of the chronic cough medical history.

### 7.6 Prior and Concomitant Medications

Prior medications are all those medications that are not concomitant (for which there is enough information to determine that the medication was stopped prior to the first dose of study treatment). Concomitant medications are those medications that begin after the first dose of study treatment or are present at baseline but continue after the first dose of study treatment. Medications missing both start and stop dates or having a start date prior to the start of study treatment and missing stop date will be counted as concomitant medication.

## 8.0 GENERAL STATISTICAL CONSIDERATIONS

The statistical software package SAS® Version 9.4 or higher (SAS Institute, Cary, NC, USA) will be used to perform all analyses and to summarize data.

### 8.1 General Analysis Considerations

For continuous variables, descriptive statistics will include the number of subjects reflected in the calculation (n), mean, standard deviation, median, minimum and maximum. Categorical variables will be summarized using frequency counts and percentages. Treatment differences in response rates (e.g., proportion of cough frequency responders) will be estimated using the stratified Miettinen and Nurminen (M&N) method (stratified by country and sex). Treatment differences in continuous data collected over multiple study visits (e.g., changes from baseline in awake cough frequency) will be assessed using the MMRM model with treatment, visit (nominal time point), country, sex, and the visit by treatment interaction as fixed effects, and baseline value as covariates.

Individual subject data obtained from the electronic case report forms (eCRFs), central laboratory, cough monitoring data, diary data, and any derived data will be presented by subject in data listings to facilitate the investigation of tabulated values and to allow for the clinical review. In general, all tables will be presented by treatment group and listings will be displayed by sorted unique subject identifier and treatment group. A subject identification number is defined as a 3-digit site number followed by a 3-digit sequentially assigned subject id (xxx-xxx). The treatment group in the listings will be based on the planned treatment(s) as allocated by the randomization scheme.

All p-values will be rounded to 4 decimal places. If a p-value is less than 0.0001 it will be displayed as “< 0.0001”, a p-value rounding to 1 will be displayed as “> 0.9999”. Unless otherwise specified all summaries will be performed by treatment group, all efficacy analyses will be based upon the FAS and all safety analyses will be based upon the Safety Analysis Set. Demographic and baseline characteristic analyses will be based upon the FAS, Safety All Randomized Subjects. The safety and demographic tables will include a total column along with the treatment columns.

The analyses described in this plan are considered a priori, in that they have been defined prior to database lock. Any analyses not described herein performed subsequent to database lock will be considered post hoc and exploratory.

## 8.2 Determination of Sample Size

The comparisons related to the primary and key secondary endpoints will be done in a hierarchical manner to control the familywise error rate. The testing procedure will start by testing the primary endpoint and then proceed to the key secondary endpoints by following the order as specified in Section 8.9.4.

A total of 170 subjects (85/arm) in 1:1 ratio to serlopitant 5 mg or placebo will provide 90% power to detect a 25% relative reduction (placebo-adjusted ratio of 0.75) in 24-hour objective cough frequency or awake objective cough frequency using a two-sample t-test at a one-sided significance level of 0.05. This assumes that 24-hour cough frequency or awake cough frequency follows a log-normal distribution with a CV of 0.64. This sample size also considers an expected dropout rate of 15%.

The sample size calculations have been performed in nQuery Advisor + nTerim.

## 8.3 Handling of Missing Data and Excluded Therapy Use

For summary statistics results will generally be reported based upon observed data. Should a determination of treatment period (on treatment, pre-treatment) be required for AEs or concomitant medication but the corresponding date is missing, or is a partial date, the event/medication will be considered on treatment unless the portions of the date that are available indicate this is not possible.

In case of missing data for the 24-hr cough frequency and the awake cough frequency, two selected imputation approaches are specified for the sensitivity analyses (Section 9.6.5).

## 8.4 Data Handling Rules for Cough Analysis

The 24-hour cough frequency (coughs per hour) for a specified visit is calculated as:

$$\text{24-hour cough frequency} = \frac{\text{total number of cough events over 24-hour monitoring period}}{\text{Total duration (in hours) over 24-hour monitoring period}}$$

The awake cough frequency (coughs per hour) is defined as below:

$$\text{Awake cough frequency} = \frac{\text{total number of cough events during the monitoring period the subjects is awake}}{\text{Total duration (in hours) for the monitoring period the subject is awake}}$$

Awake duration (hours) is time between waking up and sleep during the 24-hour monitoring period.

The cough data will contain all cough events occurring during that 24-hour monitoring period as well as the information about “sleep time” and “awake time”. Any session with duration of

recording < 4 hours will be considered as missing. Repeated monitoring may be conducted when there is an equipment failure or an unacceptable evaluation from the initial monitoring.

In general, each 24-hour session is composed by an awake monitoring period and a sleep monitoring period. If a subject did not wake up before the end of the recording session, it will be assumed that the subject slept for the rest of the session. The session will have missing awake time, and the rest of session will be considered under the sleep monitoring period. For any session with both sleep time and awake time missing, the entire 24-hour session will be considered under the awake monitoring period, unless the session has early termination of recording.

On each collection day, the cough count, the actual cough monitoring duration (in hours), and the coughs per hour will be derived for the total 24-hour period, the awake period, and the sleep period, respectively.

The percent change in 24-hour coughs per hour at each specific visit is defined as below:

percent change in 24-hour cough frequency =

$$[(\text{change from baseline in 24-hour cough frequency} \times 100) / (\text{baseline 24-hour cough frequency})]$$

## 8.5 Adjustments for Covariates

The primary endpoint will be evaluated using a mixed effect repeated measures (MMRM) model which includes fixed effects for treatment group, visit, country, sex, the treatment-by-visit interaction, and the baseline value as a covariate. In addition, exploratory analysis of the primary endpoint will be conducted by adjusting additional covariates such as age and duration of cough in the MMRM model.

## 8.6 Examination of Subgroups

Analysis for the primary efficacy endpoint will be provided for the following subgroups of baseline factors:

- Sex (Male, Female);
- Country (USA, UK);
- Age group (18 to 60 years, over 60 years);
- Duration of cough ( $\geq 10$ ,  $< 10$  in years);
- Baseline 24-hr cough frequency ( $\geq 10$ ,  $< 10$  in coughs/hour).

For each subgroup, the similar mixed effect repeated measures (MMRM) model as the primary efficacy endpoint will be performed (Section 9.6.2.1) by subgroup variable. Descriptive summary

statistics including mean, SD, and 95% CIs will be also provided. Subsequently, subgroups may be identified on a data-driven basis, and such analyses will be considered exploratory and hypothesis generating only.

## 8.7 Multiplicity Adjustments

The study is designed to evaluate the efficacy profile of serlopitant 5 mg versus placebo. The sequential testing procedure will be employed to control the overall Type I error rate at 5% with respect to multiple comparisons for the primary and key secondary endpoints. The hypothesis testing procedure will be done in a hierarchical order as specified below:

- H1: Change from baseline in 24-hour objective cough frequency after 12 weeks (Day 84) of treatment.
- H2: Change from baseline in awake objective cough frequency after 12 weeks (Day 84) of treatment
- H3: Proportion of subjects with  $\geq 30\%$  reduction in 24-hour objective cough frequency per hour at Week 12 (Day 84)
- H4: Proportion of subjects with  $\geq 30\%$  reduction in awake objective cough frequency per hour at Week 12 (Day 84)
- H5: Change from Baseline in cough severity visual analog scale (VAS) at Week 12 (Day 84)

First, the test ranked as first will be tested and the difference will be declared statistically significant if the one-sided p value is less than 0.05. Second, in case that the difference for the first comparison is statistically significant, the comparison ranked as second will be tested, and the difference will be declared statistically significant if the one-sided p-value is less than 0.05. The testing will continue as long as the previously ranked objective was statistically significant.

All other efficacy variables will be tested at the 0.05 level of significance without multiplicity adjustment.

## 9.0 STATISTICAL ANALYSES

### 9.1 Subject Disposition

The disposition of subjects will be summarized by treatment group. The number and percentage of subjects who completed the study and the number and percentage of subjects who were withdrawn will be presented. Subjects who discontinued prematurely will be summarized by number and percentage by reason for discontinuation as specified in the eCRFs.

Protocol deviations will be listed.

## 9.2 Eligibility Assessments

Subject's eligibility assessments will be listed.

## 9.3 Demographic and Baseline Information

### 9.3.1 Demographic and Baseline Characteristics

Demographic and baseline characteristics will be listed and summarized by treatment group and overall. Variables include sex, age, ethnicity, race, height, weight, body mass index (BMI), and duration of chronic cough (years).

### 9.3.2 Medical History

Medical history will be listed and summarized.

### 9.3.3 Screening Laboratory Tests

Serum pregnancy test and urine drug screen data will be listed. A list of urine drug screen tests is displayed in Appendix D.

## 9.4 Prior and Concomitant Medication

Prior and concomitant medications will be coded to anatomical therapeutic class and preferred name using the WHO drug dictionary. Listings and tabular summary of prior and concomitant medications will be presented.

All medications will be classified using the Anatomical Therapeutic Chemical (ATC) classification codes and preferred drug names from the World Health Organization Drug Dictionary (WHO Drug B2 DDE 2017-09-01)

For the medications recorded on CRF page "Prior and Concomitant Medications", medications with a stop date before the first date of study drug dosing will be considered prior medications. Medications with start date or stop date on or after the first date of study drug dosing will be considered concomitant medications.

Prior medications and concomitant medications will be presented in tabular form using the ATC Level 2 (pharmacological subgroup) and preferred term (PT). Frequencies and percentages will be presented by treatment group and overall. The tables will be sorted by overall descending frequency of ATC Level 2, and then, within an ATC Level, by overall descending frequency of PT.

### Partial or Missing Medication Start and Stop Dates

If the medication start date is incomplete, then it will be imputed as follows for the purpose of determining concomitance only:

- If the start date is completely missing, the start date will be equal to the first dose date. However, if the stop date is not missing and is before the first dose date, then the stop date will be used instead.
- If the start day is missing, the first day of the month will be used.
- If the start day and month are missing, then the first day of the first month (January) will be used.

If the medication stop date is partial, then it will be imputed as follows for the purpose of determining concomitance only:

- If the stop date is completely missing and the medication is not ongoing, the stop date will be equal to the last dose date or date of completion/withdrawal, whichever is the latest.
- If the stop day is missing, the last day of the month will be used.
- If the stop day and month are missing, then the last day of the last month (December) will be used.

The aforementioned missing or partial data handling rules will be applied to the summary tables. The recorded missing or partial date values will be presented in the listings.

### 9.5 Study Treatment Exposure and Adherence

Percent compliance will be calculated for each subject as below:

$$\text{Percent Compliance} = \frac{\text{Number of Days on Therapy}}{\text{Number of Days Should Be on Therapy}} \times 100\%$$

A day within the study will be considered an “On-Therapy” day if the participant takes all required medication. If a subject misses a daily dose, that day is not considered an On-Therapy day.

Overall treatment adherence (%) will be also calculated as below:

Overall treatment Adherence (%) =  $100\% * (\text{Total number of tablets dispensed} - \text{Total number of tablets returned}) / \text{Total expected number of tablets taken during the treatment period}$

The duration of exposure to study medication for each participant will be evaluated by calculating the number of days on therapy. Duration of exposure, percent compliance, and overall treatment adherence (%) will be summarized by treatment group using descriptive statistics (mean, SD, median, minimum, and maximum) for the safety analysis set.

## 9.6 Efficacy Analyses

For efficacy endpoints, the analysis on FAS will be considered as the primary analysis.

### 9.6.1 Statistical Hypotheses and Tests

The study is designed to evaluate, the efficacy of serlopitant 5 mg relative to placebo. The primary hypothesis for this trial is that serlopitant is superior to placebo with respect to the mean change from baseline in 24-hour cough frequency (on the log scale).

Symbolically, the hypotheses for serlopitant 5 mg compared to placebo can be written as:

$$H_0: \mu_{SP, \text{Week 12}} - \mu_{SP, \text{Baseline}} = \mu_{PL, \text{Week 12}} - \mu_{PL, \text{Baseline}}$$

$$H_A: \mu_{SP, \text{Week 12}} - \mu_{SP, \text{Baseline}} < \mu_{PL, \text{Week 12}} - \mu_{PL, \text{Baseline}}$$

where  $\mu_{SP}$  and  $\mu_{PL}$  represent the mean values at Week 12 for serlopitant 5 mg and placebo, respectively.

As the primary endpoint, cough frequency, is to be analyzed on the log scale the null hypothesis relates to the ratio of Week 12/Baseline for serlopitant 5 mg being the same as that for placebo, and the alternative hypothesis being that the ratio of Week 12/Baseline for serlopitant 5 mg is smaller than the ratio for placebo.

A family wise error rate will be controlled to adjust for multiplicity for the comparison of serlopitant 5 mg to placebo on the primary and key efficacy endpoints in a hierarchical manner (see details in [Section 8.5](#)). One-sided p-values at 0.05 significance level will be used.

### 9.6.2 Primary Endpoint

The primary endpoint of the study is the change from baseline in 24-hour objective cough frequency after 12 weeks (Day 84) of treatment.

Cough monitoring is conducted for Baseline (Study Day -1) and 24 hours after administration of the study drug on Days 28, 56, 84, and 112. An independent cough monitoring analysis center

will provide documentation of the time of each cough event over the 24-hour period, as well as the time when the subject goes to sleep and the time the subject awakens.

A negative result indicates a decrease in cough frequency, while a positive result indicates an increase in cough frequency. The Baseline cough frequency is derived from the cough monitoring performed at Baseline Visit (Study Day -1), and the post-dose cough frequency is derived from the cough monitoring performed on Days 28, 56, 84, and 112. Change from baseline and percent change in 24-hour objective cough frequency will be calculated for each visit. For descriptive summary only, the percent change from baseline will be capped at 200% for any value > 200%.

### 9.6.2.1 Analyses of Primary Endpoint

#### A. Primary Analysis - Mixed Model Repeated Measures Analysis of Log Transformed 24-hour Cough Frequency:

As the change in 24-hour cough frequency may have a skewed and wide distribution, the primary analysis for the primary endpoint will be on the natural log scale of the cough frequency data. The difference between serlopitant 5 mg and placebo will be estimated using a mixed effect repeated measures (MMRM) model. The model will include fixed effects for treatment group, visit, country, sex, the treatment-by-visit interaction, and the log-transformed baseline value as a covariate. The MMRM model will use all available 24-hour cough frequency data on Day 28, 56, and 84. An unstructured covariance structure will be applied for MMRM. In case the model will not converge with the unstructured covariance structure, the heterogeneous compound symmetry (CSH) will be used instead. Furthermore, if the model fails to converge with CSH, the heterogeneous Toeplitz structure (TOEPH) will be used. If the unstructured covariance structure will be used, the denominator degrees of freedom will be computed using the Kenward-Roger method. In case of other covariance structures, the BETWITHIN (SAS®) option will be used for the denominator degrees of freedom. Contrasts will be constructed to compare each of the three serlopitant treatment groups to the placebo group at each visit. The least-squares (LS) mean change from baseline (on the log scale) with the associated standard errors will be displayed for each treatment group. Estimated treatment differences (serlopitant vs. placebo) along with corresponding one-sided 95% CIs and p-values will also be presented at each post-baseline timepoint.

In addition, the geometric mean of 24-hour cough frequency will be presented by treatment and by visit. The percent difference change between serlopitant and placebo will be estimated by  $100(e^{\text{diff}} - 1)$ , where diff is the difference provided by the analysis of the log-transformed variable. A sample of SAS code for MMRM analysis is provided in Appendix A.

An observation of zero coughs per hour will be replaced by a cough rate of 0.1 for the calculation of geometric means.

Missing data, in the assessment of the primary hypothesis, is assumed as missing at random (MAR). This assumption will be assessed with a missing data sensitivity analysis (see Section 9.6.5 Sensitivity analysis of the primary endpoint).

### **B. Secondary Analysis - Mixed Model Repeated Measures Analysis of 24-hour Cough Frequency on the Original Scale:**

The changes from baseline in 24-hour cough frequency on the original scale will be also analyzed using the same MMRM model, fitting terms for treatment group, visit, country, sex, the treatment-by-visit interaction, and the Baseline value as a covariate. The least-squares (LS) mean change from baseline (on the original scale) with the associated standard errors will be displayed for each treatment group. Estimated treatment differences (serlopitant 5 mg vs. placebo) along with corresponding one-sided 95% CIs and p-values will also be presented for each treatment group at each post-baseline timepoint. This analysis will be considered as secondary analysis for primary endpoint.

### **C. Secondary Analysis - ANCOVA Analysis on Ranks of Log Transformed 24-hour Cough Frequency at Week 12:**

Additionally, the ranked scores of the primary endpoint (on the natural log scale) at Week 12 (Day 84) will be analyzed using an analysis of covariance (ANCOVA) model with fixed effects for treatment group, visit, country, sex, and the log-transformed baseline value as a covariate. This analysis will be considered as secondary analysis for primary endpoint. A sample of SAS code for ANCOVA analysis for ranked data is provided in Appendix A.

## **9.6.3 Key Secondary Endpoints**

### **9.6.3.1 Awake Objective Cough Frequency**

Analyses for awake objective cough frequency will proceed in the same manner as the analyses indicated in Section 9.6.2.1 above at for the Primary Efficacy endpoint.

### **9.6.3.2 Cough Frequency Responder Analysis**

Two key cough frequency responder endpoints are:

- Proportion of subjects with  $\geq 30\%$  reduction in 24-hour objective cough frequency per hour at Week 12 (Day 84)
- Proportion of subjects with  $\geq 30\%$  reduction in awake objective cough frequency per hour at Week 12 (Day 84)

The proportion of participants with  $\geq 30\%$  of reduction from baseline in 24-hour cough frequency at each specific visit is the number of participants with  $\leq -30\%$  change in 24-hour cough frequency divided by the total number of participants with available data at the specific visit. Similar definition will be applied for awake cough frequency.

In addition, the exploratory analyses of  $\geq 50\%$  of reduction and  $\geq 70\%$  of reduction will be conducted for both 24-hour and awake cough frequency.

Moreover, for categorical analysis, three responder variables for 24-hour or awake objective cough frequency will be defined based on the magnitude of the percent change from baseline.

$\geq 70\%$  Reduction = 1 if Percent Change from Baseline in cough frequency at each visit  $\leq -70.0\%$ ; 0 Otherwise

$\geq 50\%$  Reduction = 1 if Percent Change from Baseline in cough frequency at each visit  $\leq -50.0\%$ ; 0 Otherwise

$\geq 30\%$  Reduction = 1 if Percent Change from Baseline in cough frequency at each visit  $\leq -30.0\%$ ; 0 Otherwise

Note that these responder definitions are not mutually exclusive. In particular, a subject who achieves a 1 for  $\geq 70\%$  Reduction, will, by definition, be classified as a 1 for  $\geq 50\%$  Reduction and  $\geq 30\%$  Reduction. The count and percentage of subjects who meet the responder criteria for  $\geq 70\%$  Reduction,  $\geq 50\%$  Reduction, and  $\geq 30\%$  Reduction will be summarized by treatment group and by visit.

For cough frequency responder endpoint, the primary analysis for the comparison of response rates between each of the serlopitant 5 mg and placebo will be conducted using the stratified Cochran Mantel Haenszel (CMH) test (stratified by country and sex, unless stated otherwise). Missing data will be categorized as discontinued or missing. Furthermore, the differences in proportions between two treatment groups will be estimated using the stratified Miettinen and Nurminen (M&N) method. A sample of SAS code for categorical analysis is provided in Appendix A.

In addition, the responder endpoint will be analyzed by a generalized linear mixed model (GLMM) with treatment, visit, country, sex, and treatment by visit interaction as fixed effects. Visit ordering will be treated as a repeated measure within subjects. The GLMM model will use all available cough frequency data on Day 28, 56, and 84. The least-squares (LS) mean proportions with the associated standard errors will be displayed for each treatment group. Estimated odds ratio (serlopitant vs. placebo) along with corresponding one-sided 95% CIs and p-values will also be presented at each post-baseline timepoint.

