- Proportion of subjects with $\geq 30\%$ reduction in awake objective cough frequency per hour at Week 12
- Change from baseline in Cough Severity Visual Analog Scale (VAS) at Week 12

Other Secondary

- Change from baseline in 24-hour objective cough frequency after 4 and 8 weeks (Day 28 and 56) of treatment
- Change from baseline in awake objective cough frequency after 4 and 8 weeks (Day 28 and 56) of treatment
- Change from baseline in 24-hour objective cough frequency at the Follow-Up visit (Day 112)
- Change from baseline in sleep objective cough frequency after 4, 8 and 12 weeks (Day 28, 56 and 84) of treatment
- Change from Baseline in Cough Severity Visual Analog Scale (VAS) at Weeks 4 and 8
- Change from Baseline in Leicester Cough Questionnaire (LCQ) individual Domain and Total scores
- Patient's Global Impression of Change (PGIC)
- Clinician's Global Impression of Change (CGIC)

Statistical approaches for analysis of the secondary endpoints will be detailed in the SAP. The continuous secondary efficacy endpoints will be analyzed using the same MMRM model as used for the primary efficacy analysis.

The categorical secondary efficacy endpoints will be analyzed using the stratified Miettinen and Nurminen (M&N) method, adjusting for gender and country.

Table 2 Analysis Strategy for Primary and Key Secondary Efficacy Endpoints

Endpoint	Statistical Method	Analysis Population	Missing Data Approach
Primary Efficacy Endpoint			
Change from baseline in 24-hour objective cough frequency after 12 weeks (Day 84) of treatment	MMRM	FAS	Observed data only
			Reference-based imputation & Tipping-point approach
Key Secondary Efficacy Endpoints			
Change from baseline in awake objective cough frequency after 12 weeks (Day 84) of treatment	MMRM	FAS	Observed data only
Proportion of participants with $\geq 30\%$ reduction in 24-hour objective cough frequency after 12 weeks (Day 84) of treatment	Stratified Miettinen and Nurminen (M&N)	FAS	Observed data only
Proportion of participants with $\geq 30\%$ reduction in awake objective cough frequency after 12 weeks (Day 84) of treatment	Stratified Miettinen and Nurminen (M&N)	FAS	Observed data only
Change from baseline in VAS after 12 weeks (Day 84) of treatment	MMRM	FAS	Observed data only

MMRM = Mixed Model Repeated Measures; GLMM= Generalized Linear Mixed Model; VAS = Visual Analogue Scales; FAS = Full Analysis set;

8.9.4 *Multiplicity Adjustment*

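### Responder tests H3 and H4 adjust for country and sex but not baseline cough rate: they are valid, but lose power by an amount that depends on a correlation the plan does not state

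*SAP*

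**What the plan says.** SAP 8.7 tests five hypotheses in a fixed sequence, and at each step "the difference will be declared statistically significant if the one-sided p value is less than 0.05". The order is 24-hour rate (H1), awake rate (H2), 30% responders on the 24-hour rate (H3), 30% responders on the awake rate (H4), then VAS (H5).

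- **H1** (SAP 9.6.2.1): "The model will include fixed effects for treatment group, visit, country, sex, the treatment-by-visit interaction, and the log-transformed baseline value as a covariate".
- **H2 and H5** (SAP 9.6.3.1 and 9.6.3.3) follow the H1 analysis. The covariate is the baseline awake rate for H2 and baseline VAS for H5.
- **H3 and H4** (SAP 9.6.3.2): the primary comparison "will be conducted using the stratified Cochran Mantel Haenszel (CMH) test (stratified by country and sex, unless stated otherwise". M&N supplies the difference in proportions.
- **Supporting model** (SAP 9.6.3.2): a "generalized linear mixed model (GLMM) with treatment, visit, country, sex, and treatment by visit interaction as fixed effects".
- **Protocol 8.9.3**: "The categorical secondary efficacy endpoints will be analyzed using the stratified Miettinen and Nurminen (M&N) method, adjusting for gender and country".

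The sample code in SAP Appendix A agrees on baseline: neither the CMH table nor the GLMM model statement contains it. The GLMM code also omits sex, which the text lists.

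On sample size, SAP 8.2 says "A total of 170 subjects (85/arm) in 1:1 ratio to serlopitant 5 mg or placebo will provide 90% power" for "a 25% relative reduction (placebo-adjusted ratio of 0.75", "using a two-sample t-test at a one-sided significance level of 0.05". That statement covers 24-hour or awake cough frequency. No response rates and no power are given for H3 or H4.

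**The concern.** A responder is defined by percent change from the subject's own baseline, which can look like an adjustment for baseline. It is not a full one. Baseline is a single recording session. A subject who happened to record high that day tends to fall back and is more likely to be counted as a responder; one who recorded low is less likely. The primary model deals with this by including log baseline even though its outcome is already a change from baseline. H3 and H4 dichotomise change on the same scale and recordings without that term.

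What is at stake is power at two alpha-controlled steps. Both precede VAS, so a miss at either also stops H5 from being tested. In addition, a chance difference in baseline between arms is handled in H1 and H2 but only partly in H3 and H4.

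**Working it through.** **1. The plan's sample size reproduces.** Inputs from SAP 8.2: ratio 0.75, CV 0.64, one-sided 0.05, 90% power, 15% dropout.

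- Log SD = sqrt(ln(1 + 0.64²)) = sqrt(0.3433) = 0.586; effect = ln(0.75) = -0.2877.
- n per arm = 2 × (1.645 + 1.282)² × 0.3433 / 0.2877² = 71.05, so 72.
- 72 / 0.85 = 84.7, so 85 per arm and 170 in total. Exact t-test power at 72 per arm is 90.1%.

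**2. The responder endpoint under the same inputs.** Response means log change ≤ ln(0.70) = -0.3567. Take 0.586 as the SD of log change and assume a placebo mean log change of -0.2 (not in the documents).

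- Placebo: Φ((-0.3567 + 0.2) / 0.586) = Φ(-0.267) = 39.5%.
- Serlopitant: Φ((-0.3567 + 0.4877) / 0.586) = Φ(0.224) = 58.8%.
- Unadjusted two-proportion power at 72 per arm is 75.7%. It stays between 73.8% and 75.7% for placebo changes from 0 to -0.4.

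**3. How strongly baseline predicts change.** With equal variances at the two visits and correlation rho,

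corr(change, baseline) = (rho - 1) / sqrt(2(1 - rho)) = -sqrt((1 - rho)/2),

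which is -0.50 at rho 0.5, -0.39 at 0.7 and -0.32 at 0.8.

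**4. Power with and without baseline.** Simulation with bivariate normal log rates and 72 per arm. CMH (country by sex) is compared with logistic regression on treatment, country, sex and log baseline, all at one-sided 0.05. Rho, placebo change and the mix of strata are assumptions.

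Reading A takes CV 0.64 as the spread of log change (placebo log change -0.2, 16,000 trials per setting, likelihood-ratio tests, Monte Carlo error about 0.3 points):

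| rho | CMH | Logistic, no baseline | Logistic with baseline | Gain over CMH | Gain over logistic without baseline |
|---|---|---|---|---|---|
| 0.3 | 74.6% | 75.7% | 84.2% | 9.6 | 8.5 |
| 0.5 | 75.5% | 76.6% | 82.0% | 6.5 | 5.4 |
| 0.6 | 74.8% | 75.6% | 80.6% | 5.8 | 5.0 |
| 0.7 | 75.3% | 76.3% | 79.3% | 4.0 | 3.0 |
| 0.8 | 74.7% | 75.9% | 78.1% | 3.4 | 2.2 |
| 0.9 | 74.8% | 75.8% | 76.8% | 2.0 | 1.0 |

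At rho 0.5, varying the placebo change from 0 to -0.35 moves the gain over CMH between 6.5 and 7.4 points.

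Reading B takes CV 0.64 as the spread at each visit (placebo log change -0.1 or -0.3, 3,000 trials per setting, score test):

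| rho | CMH | Logistic with baseline |
|---|---|---|
| 0.5 | 74% | 81% |
| 0.6 | 81-83% | 86-87% |
| 0.7 | 91% | 93-94% |
| 0.8 | 97% | 98% |

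The readings coincide at rho 0.5, because SD of change = SD × sqrt(2(1 - rho)).

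**5. Type I error.** At rho 0.5 it is 4.8% for CMH and 5.2% for the adjusted test. It stayed within about 4-6% for both across the checks.

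**6. Which rho is plausible.** The only hint is Protocol 1.1, which puts awake rates at about 20 to several hundred per hour. If 20-300 covers the central 90-95% of subjects (an assumption), log SD is ln(15)/3.29 = 0.82 or ln(15)/4 = 0.68. Under reading A, rho = 1 - 0.3433/(2 × SD²), or about 0.75 or 0.63. Upper limits of 200 to 500 widen this to 0.48-0.82.

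**The case against.** CMH stratified by exactly the randomisation factors is a standard, valid test that needs no model for how response depends on baseline. Baseline level already enters through percent change, and the fully baseline-adjusted analyses of the same recordings, H1 and H2, are tested first. All of that stands. Choosing a covariate-adjusted test is a matter of efficiency.

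The size is also open to challenge. At rho 0.5 the gain is about 7 points, but the rough hint in the protocol points somewhat higher, where the gain is smaller. Part of the gain, about 1 point or less, comes from replacing CMH with a likelihood-based test. This stands too, which is why a range is given.

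Four stronger readings are tempting and are not supported:

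- **That every other confirmatory test adjusts for baseline cough rate.** H1 and H2 do; H5 adjusts for baseline VAS.
- **That H3 and H4 are biased or inflate type I error.** The simulated error rates are near 5% for both approaches.
- **That the plan's 90% power is contradicted.** That figure is for cough frequency, and it reproduces.
- **That the loss is a fixed 7 points.** It depends on a correlation the documents do not give.

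**Conclusion.** The omission is real: neither the H3/H4 test, in either document, nor the supporting GLMM contains baseline cough rate. It is lost efficiency in a valid test. Against CMH, adjusting for log baseline gains about 7 points of power at rho 0.5, 3-6 at 0.6, 2-4 at 0.7 and 1-3 at 0.8. The ranges span both readings of the CV.

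These figures rest on log-normal rates with equal variance at both visits, the plan's effect and dropout, and assumed values for rho and the placebo change. The gain reaches 5 points only for rho up to about 0.6. Lower power at H3 or H4 also lowers the chance of reaching H5, but the two losses should not be added, because both tests use the same recordings. The change is worth making because it is cheap.

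**What to change.** Before unblinding:

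1. In SAP 9.6.3.2, test H3 and H4 at Day 84 with a logistic model containing treatment, country, sex and the log-transformed baseline rate of the same measure (24-hour for H3, awake for H4). Name the one-sided score test for treatment as the decision test.
2. Report the baseline-standardised difference in response proportions, and name in advance either a delta-method or a bootstrap confidence interval.
3. Keep stratified CMH and M&N as supportive analyses.
4. Add log baseline to the GLMM in both text and Appendix A code, and add SEX to the code to match the text.
5. Align Protocol 8.9.3 and Table 2 with the SAP, since the two documents now name different responder methods.

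The cost is some wording and a few lines of SAS. Log baseline is already derived for the primary model, and no new data are needed. The downside is small: the p-value for H3 and H4 becomes model-based, and the logistic coefficient is a conditional odds ratio, so standardisation is needed to keep the reported effect marginal.
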